### Non-Inferiority

For coprimary objective 2 the assumption is that SCR is 50% in the reference method ( $p2 = 0.50$ ). If the SCR of the investigational is no less than 5 percentage points worse ( $\delta_0 = -0.05$ ) than the reference, it will be considered non-inferior. Substituting these figures into the statistical hypotheses gives

$$H0: p1 - p2 \leq -0.05 \text{ versus } H1: p1 - p2 > -0.05$$

The overall power for STEP 1 is calculated assuming that coprimary objectives 1 and 2 are independent; therefore overall power is 0.979 (0.98768\*0.99136) as stated in the protocol (section 10.2)

A sample size of up to 385 participants of study ARCT-154-J01, who received ARCT-154 vaccine booster, provided evaluable pre- and post-vaccination blood samples, and did not have SARS-CoV-2 infection and protocol deviations that impact on immunogenicity assessment (PPS-1), and up to 560 participants in the ARCT-2303 (groups 2a and 2b) provides approximately 99% power (n=350 and n=500 in the two groups if there is drop out of approximately 10%) to demonstrate each of the 2 coprimary objectives; therefore, there is at least 97% overall power to demonstrate the two coprimary objectives, 1 and 2.

### STEP 2

If coprimary objectives 1 and 2 are met, then the second step will be assessing the noninferiority of immune response after co-administration and standalone administration of ARCT-2303 and Flucelvax Quadrivalent vaccines. The following null hypotheses will be tested:

$$H03: \text{Day 29 GMT QIV}_{\text{QIV+ARCT-2303}} / \text{Day 29 GMT QIV}_{\text{QIV+Placebo}} \leq 0.67$$

(Group 1a vs 3a, i.e. co-admin group recipients vs standalone ARCT-2303 recipients)

$$H04: \text{Day 29 GMT ARCT-2303}_{\text{QIV+ARCT-2303}} / \text{Day 29 GMT ARCT-2303}_{\text{ARCT-2303+Placebo}} \leq 0.67$$

(Group 1a vs 2a, i.e. co-admin group recipients vs standalone Flucelvax recipients)

Statistical power is calculated assuming that:

- GMT ratios are expected to be 1.0
- the common standard deviation is expected to be 0.60 in the log10 scale.

### Two-Sample T-Tests for Non-Inferiority Assuming Equal Variance

Solve For:	Power						
Difference:	$\delta = \mu_1 - \mu_2 = Mt - Mr$						
Higher Means Are:	Better						
Hypotheses:	$H0: \delta \leq -NIM$ vs. $H1: \delta > -NIM$						
Power	N1	N2	N	-NIM	$\delta$	$\sigma$	Alpha
0.97578	360	360	720	-0.176	0	0.6	0.025

Power      The probability of rejecting a false null hypothesis when the alternative hypothesis is true.

N1 and N2      The number of items sampled from each population.

N      The total sample size.  $N = N1 + N2$ .

-NIM	The magnitude and direction of the margin of non-inferiority. Since higher means are better, this value is negative and is the distance below the reference mean that is still considered non-inferior.
$\delta$	The difference between the treatment and reference means at which power and sample size calculations are made. $\Delta = \mu_1 - \mu_2 = Mt - Mr$ .
$\sigma$	The assumed population standard deviation for each of the two groups.
Alpha	The probability of rejecting a true null hypothesis.

No adjustment for multiplicity is planned, as both H03 and H04 (all 5 null hypotheses: 4 strains for QIV and 1 strain for ARCT-2303) must be rejected to declare noninferiority of immune response.

The overall power for STEP 2 is calculated assuming that objectives 3 and 4 are independent therefore overall power is 0.885 (0.97578 to the power of 5) as stated in the protocol (section 10.2)

A sample size of 400 participants per group (groups 1a, 2a, and 3a) provides 97.5 power ( $n=360$  per group if there is drop out is approximately 10%) to demonstrate noninferiority for each one of the 5 strains (4 strains for influenza vaccine and 1 strain for ARCT-2303); therefore, there is at least 88% overall power to demonstrate all of the noninferiority objectives.

The overall power to demonstrate all 4 coprimary objectives is at least 85% ( $0.979*0.885=0.86$ ).

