If coprimary objectives 1 and 2 are met, then the second step will be assessing the noninferiority of immune response after co-administration and standalone administration of ARCT-2303 and Flucelvax Quadrivalent vaccines.

The noninferiority objectives for the co-administration are:

3) vaccination with Flucelvax Quadrivalent, when given concomitantly with ARCT-2303, compared to that of Flucelvax Quadrivalent, when given standalone

NI of GMT QIV+ ARCT-2303 to GMT QIV + Placebo (Group 1a vs Group 3a)

4) vaccination with ARCT-2303, when given concomitantly with Flucelvax Quadrivalent, compared to that of ARCT-2303, when given standalone

NI of GMT ARCT-2303 + QIV to GMT ARCT-2303+placebo (Group 1a vs Group 2a)

The noninferiority margin is defined as 0.67 for the GMTs ratios.

Assumptions for the above calculations are:

the GMT ratios between the

a-Flucelvax Quadrivalent, when given concomitantly with ARCT-2303, compared to Flucelvax Quadrivalent, when given standalone,

b- ARCT-2303, when given concomitantly with Flucelvax Quadrivalent, compared to ARCT-2303, when given standalone,

is expected to be 1.0 and the common standard deviation is expected to be 0.60 in the \log_{10} scale.

A sample size of 400 participants per group (Groups 1a, 2a, and 3a) provides 97.5% power (n=360 per group if there is dropout of approximately 10%) to demonstrate noninferiority for each one of the 5 strains (4 strains for influenza vaccine and 1 strain for ARCT-2303); therefore, there is at least 88% overall power to demonstrate all of the noninferiority objectives. The overall power to demonstrate all 4 coprimary objectives is at least 85%.

Populations for Analyses

The analysis sets are defined in [Table 8](#).

CONFIDENTIAL

Table 8 Analysis Sets

| Analysis Set | Description |
|---|--|
| Enrolled Set | All screened participants who provided informed consent, received a participant ID, and were randomized. |
| Exposed Set / Intent to Treat (ITT) Analysis Set | All participants who received at least one dose of a study vaccine. The ITT Analysis Set will be analyzed according to the vaccine assigned. |
| Modified ITT Analysis Set | All participants who are randomized, received at least one dose of a study vaccine and provided at least one post-baseline immunogenicity assessment. The mITT will be analyzed according to vaccine assigned. |

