### 8.1.3 Noninferiority for the influenza vaccine strains on Day 29 based on the HI assay

If simple superiority of the GMT and noninferiority of the SCR are concluded in the 2 tests discussed above, immune response for each influenza vaccine strain based on the HI assay

after co-administration of ARCT-2303 and Flucelvax Quadrivalent will be compared to immune response after standalone administration of Flucelvax Quadrivalent

$$\text{GMT ratio} = \frac{\text{GMT}_{\text{QIV+ARCT-2303(Day 29)}}}{\text{GMT}_{\text{QIV+Placebo (Day 29)}}}$$

The analysis of the GMT ratio will be done using ANCOVA, as described in Section 3.3.2. Non-inferiority will be concluded if the lower limit of the 2-sided 95% CI for the GMT ratio is higher than 0.67 for all 4 influenza strains.

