## 13 APPENDIX

### 13.1 Sample Size Calculation

#### **STEP 1**

Objective 1:

The coprimary objective of simple superiority of the ARCT-2303 vaccine booster (groups 2a and 2b) compared to the ARCT-154 booster for the Omicron XBB.1.5 subvariant

Superiority of  $GMT_{ARCT-2303 \text{ (booster)}}$  to  $GMT_{ARCT-154 \text{ (booster)}}$

The superiority margin for the Omicron XBB.1.5 subvariant is defined as 1.0 for the GMTs ratio, thus the lower limit of the 2-sided 95% CI for GMT ratios (ARCT-2303/ARCT-154) is higher than 1.0.

Statistical power for the coprimary objective 1 is calculated assuming that:

- the GMT ratio between ARCT-2303 (Day 29) and ARCT-154 (booster; ARCT-154-J01 study) (Day 29) groups is 1.5,
- the common standard deviation is expected to be 0.60 in the log10 scale.

If the GMT ratio is 1.5 that means that the difference of the 2 means in log scale is 0.176 ( $\delta$ ). The differences between those two means is equal to 0 (=SM) when the GMT ratio is equal to 1.

Numeric Results for an Equal-Variance T-Test

Solve For:	Power						
Difference:	$\delta = \mu_1 - \mu_2 = Mt - Mr$						
Higher Means Are:	Better						
Hypotheses:	$H_0: \delta \leq SM \text{ vs. } H_1: \delta > SM$						
Power	N1	N2	N	SM	$\delta$	$\sigma$	Alpha
0.98768	500	350	850	0	0.176	0.6	0.025

Power	The probability of rejecting a false null hypothesis when the alternative hypothesis is true.
N1 and N2	The number of items sampled from each population.
N	The total sample size. $N = N_1 + N_2$ .
SM	The magnitude of the margin of superiority. Since higher means are better, this value is positive and is the distance above the reference mean that is required to be considered superior.
$\delta$	The difference between the treatment and reference means at which power and sample size calculations are made. $\delta = \mu_1 - \mu_2 = Mt - Mr$ .
$\sigma$	The assumed population standard deviation for each of the two groups.
Alpha	The probability of rejecting a true null hypothesis. One-sided Alpha=0.025 that is equivalent to Two-sided Alpha=0.05

The null ( $H_0$ ) and alternative ( $H_1$ ) hypotheses for one-sided tests are defined as

$H_0: \mu_1 - \mu_2 \leq \delta_0$  versus  $H_1: \mu_1 - \mu_2 > \delta_0$   
or equivalently

$H_0: \delta \leq \delta_0$  versus  $H_1: \delta > \delta_0$ .

Rejecting this test implies that the mean difference is larger than the value  $\delta_0$ .

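### The Step 2 power run in SAP 13.1 uses a margin of about 2/3 while the decision limit is 0.67, so the stated 97.5% and at-least-88% power figures are slightly too high (minor)

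*SAP*

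**What the plan says.** Protocol section 10.2 fixes the limit for the co-administration comparisons: "The noninferiority margin is defined as 0.67 for the GMTs ratios". The hypotheses in protocol 10.1 and SAP 3.3.1 use the same number. So do the decision rules: SAP 8.1.3 concludes noninferiority "if the lower limit of the 2-sided 95% CI for the GMT ratio is higher than 0.67 for all 4 influenza strains", and SAP 8.1.4 applies 0.67 to the XBB.1.5 titer.

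The power calculation is in SAP 13.1, Step 2. It assumes that "GMT ratios are expected to be 1.0" and that the common SD is 0.60 on the log10 scale. The result row, in the order power, N1, N2, N, margin, difference, SD, alpha, reads "0.97578 360 360 720 -0.176 0 0.6 0.025". Independence is assumed, and the per-test figure is compounded over the five tests: "overall power is 0.885 (0.97578 to the power of 5"). Protocol 10.2, the synopsis and SAP 13.1 then state 97.5% power per comparison and that "there is at least 88% overall power to demonstrate all of the noninferiority objectives". For all four coprimary objectives they state at least 85%, which SAP 13.1 supports with the product of 0.979 and 0.885, printed as 0.86.

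**The concern.** The margin in the power run is not the margin that decides success. A log10 margin of -0.176 corresponds to a ratio of 0.6668, whereas log10(0.67) is -0.1739. The power was therefore computed against a limit slightly easier to clear than the one to be applied. The error per test is small, but all five comparisons must succeed, so it is compounded in the joint figure.

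What is at stake is the accuracy of two stated numbers. The 88% is worded as a floor, and the plan's own inputs do not reach it once the operative limit is used. Anyone who re-runs the table from the protocol's stated margin will get a different answer from the one printed.

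**Working it through.** **Inputs**
- Evaluable participants: 360 per group (400 less about 10% dropout; protocol 10.2, SAP 13.1).
- Common SD: 0.60 on the log10 scale; true GMT ratio 1.0, so the true difference is 0 (both documents).
- Alpha: one-sided 0.025 (SAP 13.1, Step 2 table; the Step 1 note explains "One-sided Alpha=0.025 that is equivalent to Two-sided Alpha=0.05").
- Margin in the power run: -0.176 (SAP 13.1). Decision limit: 0.67 (protocol 10.1 and 10.2; SAP 3.3.1, 8.1.3 and 8.1.4).
- Tests: five, all required, treated as independent (SAP 13.1).
- Step 1 power: 0.98768 × 0.99136 = 0.979 (SAP 13.1).

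**Method**

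Two-sample equal-variance t-test, power from the noncentral t distribution with 360 + 360 - 2 = 718 degrees of freedom.
- Standard error = 0.6 × √(2/360) = 0.04472.
- Critical value t(0.975; 718) = 1.9633.
- Noncentrality = |log10 margin| / 0.04472.
- Joint Step 2 power = (per-test power)^5; overall power = joint power × 0.979.

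**Reproducing the plan's figures (margin -0.176)**
- Noncentrality = 0.176 / 0.04472 = 3.935.
- Per-test power = 0.9756 (SAP: 0.97578).
- Five tests: 0.884 (SAP: 0.885).
- Entering log10(2/3) = -0.17609 without rounding gives 0.9757 and 0.884.

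The SAP's figures are therefore reproduced, to within 0.02 points per test and about 0.1 point jointly, at a margin of about 2/3.

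**Repeating at the decision limit (0.67)**
- log10(0.67) = -0.17393; noncentrality = 0.17393 / 0.04472 = 3.889.
- Per-test power = 0.9728.
- Five tests: 0.871.
- All four coprimary objectives: 0.871 × 0.979 = 0.853.

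| Quantity | Stated | Recomputed at -0.176 | Recomputed at log10(0.67) |
|---|---|---|---|
| Per comparison | 97.5% (0.97578) | 97.6% | 97.3% |
| All five comparisons | at least 88% (0.885) | 88.4% | 87.1% |
| All four coprimary objectives | at least 85% (0.86) | 86.5% | 85.3% |

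**Size in participants**

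At the 0.67 limit, 366 evaluable per group gives 88.0% jointly and 367 gives 97.5% per test. That is 6 or 7 more than the 360 assumed, or dropout of 8.5% or 8.25% from 400.

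**The case against.** The strongest reply is that this is a rounding effect. To two decimals 2/3 is 0.67, and the same appendix uses 0.176 for the log of the reciprocal ratio, 1.5. A limit printed to two decimals may simply have been entered unrounded. That is plausible, and the point does not depend on how the input arose. The documents nowhere define the limit as 2/3, however, and the decision rule uses 0.67 as printed, so the two should agree.

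A second reply is that other features of the plan could restore 88%. Three are worth weighing:
- **Correlation.** All five tests share Group 1a, and the four strain tests use the same participants, so positive correlation is plausible. Suppose correlation rho among the strain statistics and rho/2 with the COVID-19 test (assumed values; the documents give none). Simulated joint power at 0.67 is then 0.872 at rho 0, 0.875 at 0.1, 0.879 at 0.2, 0.884 at 0.3 and 0.895 at 0.5. The 88% is regained between 0.2 and 0.3.
- **ANCOVA.** The planned model adjusts for baseline titer, age and sex, and for the stratification factors. If 0.60 is the unadjusted SD, covariates explaining about 1.7% of the variance would restore 88%. The documents do not say how much variance the covariates explain.
- **Uncertainty in the inputs.** At 0.67 and 360 per group, joint power is 94.4% at SD 0.55, 88.0% at 0.595 and 76.5% at 0.65. The SD assumption matters far more than the margin.

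All three stand as reasons to treat the point as minor. None makes the stated floor true, because the SAP's run uses SD 0.60, a t-test without covariates, and independence.

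In the other direction, a reader might infer that the trial is underpowered, or that the 85% overall claim fails. The documents do not support either inference: overall power at 0.67 is 85.3% under the stated independence assumption. A bound that holds under any dependence is lower, 1 - 5 × 0.0272 - 0.0123 - 0.0086 = 84.3%. It is a worst case, and the positive correlation that the shared groups make plausible would move joint power upwards from the independence figure.

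**Conclusion.** The discrepancy is real and minor. With the SAP's own inputs and its stated independence assumption, using 0.67 lowers per-comparison power to 97.3%, which is 0.2 points below the stated 97.5% and 0.3 below the printed 0.97578. Joint power for the five comparisons falls to 87.1%, which is 0.9 points below the stated 88% floor and 1.4 below the printed 0.885. The 85% floor for all four coprimary objectives still holds under independence, at 85.3%. The documents do not settle whether the input was a slip or an unrounded 2/3. The discrepancy affects no test, no decision rule and no sample size.

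**What to change.** Re-run the Step 2 table in SAP 13.1 with the margin set to log10(0.67) = -0.1739. Then restate the power in the protocol synopsis, protocol 10.2 and SAP 13.1 as about 97.3% per comparison, about 87% for all five comparisons and about 85% for all four coprimary objectives, each of the last two marked as assuming independence. Replace the SAP's closing product with 0.979 × 0.871 = 0.853. Leave the 0.67 limit and the enrolment unchanged. The cost is wording only, with slightly less favourable stated power.

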### **STEP 3**

If objectives 1, 2, 3 and 4 are met, then secondary objectives 2 (superiority of SCR) and 1 ('super superiority' of GMTs) of the ARCT-2303 vaccine, when given as a booster dose compared to a booster dose of ARCT-154 (in study ARCT-154-J01), will be tested in a sequential manner as follows (if H05 is rejected then H06 is tested too):

H05: Day 29 SCR ARCT-2303 booster dose minus Day 29 SCR ARC-154booster  $\leq 0\%$

H06: Day 29 GMT ARCT-2303 booster dose /Day 29 GMT ARC-154booster  $\leq 1.5$

No adjustment for multiplicity is planned: H05 will be tested only if H01,02,03,04 are rejected and H06 will be tested only if H01,02,03,04,05 are rejected. No statistical power is calculated for STEP 3 as it includes only secondary objectives.
